1. Initiation of Mito-MES within 5 days since exposure to index case. To ensure that a study 10 participant met this inclusion criterion, the study participant should have had high-risk close 11 12 contact with a confirmed COVID-19 case within the past 1-4 days prior to study entry. This 13 4-day window would also allow for up to 24-hour period for initiation of intervention (mito-MES) so that mito-MES would be started within 5 days since exposure to index case; 14 2. Successfully contacted by the study team within 24 h of study team notification of the 15 16 relevant index COVID-19 case. This time window is necessary because the efficacy of PEP 17 may be dependent on the timing of its initiation. Every effort was made by the study team to 18 include study participants who would be able to initiate mito-MES as soon as possible after notification of exposure to index case of SARS-CoV-2 infection. For many study participants, 19 Mito-MES was provided immediately after informed consent so that it would be available for 20 21 immediate use after anticipated exposure to confirmed case of SARS-CoV-2. It is well established that antivirals have highest efficacy when given as soon as possible (ideally 22 within 48 hours). This design with immediate initiation of Mito-MES within 72 hours post 23 24 exposure is different than the study design in a randomized controlled Phase 2/3 EPIC-PEP 25 (Evaluation of Protease Inhibition for COVID-19 in Post-Exposure Prophylaxis) of paxlovid given within 5 days post exposure from SARS-CoV-2 that failed to demonstrate therapeutic 26

1		efficacy (unpublished data). Time of initiation of the post-exposure prophylaxis (PEP)
2		treatment is critical in the setting of emerging SARS-CoV-2 variants that may establish
3		infection in less than 5 days.
4	3.	Ineligible for FDA approved alternative treatments to prevent progression to severe viral
5		infection including COVID-19 based on established criteria
6		https://www.cdc.gov/coronavirus/2019-ncov/need-extra-precautions/people-with-medical-
7		conditions.html. Rationale: If the study participant has confirmed exposure to SARS-CoV-2,
8		the participant will be allowed to enroll only if he/she is eligible for other FDA approved
9		treatments such as monoclonal antibodies or other antivirals for reasons such as personal
10		choice, allergies or lack of availability.
11	11	Willing to follow sexual abstinence during study period or highly effective method of

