1 diagnostic test such as SARS-CoV-2 FDA approved test (can delay initiation of treatment for at 2 least 24-48 hours). If a participant has a positive SARS-CoV-2 during the study, then the participant will be allowed to continue the study only if not eligible for another FDA approved 3 treatment for COVID-19, given the potential favorable antiviral and anti-inflammatory effects of 4 5 mito-MES in SARS-CoV-2 infection. However, these participants with a positive SARS-CoV-2 6 test will not be included in the final analysis of this PEP trial. The data obtained from the participants with a positive SARS-CoV-2 test will set the foundation for future studies of use of 7 8 mito-MES as treatment for acute COVID-19. 9 Exclusion criteria for all study participants: 10 11 Participants who meet any of the following criteria at screening will be excluded from the study: 12 1. Use of Coenzyme Q10 or Vitamin E < 120 days from enrollment 13 2. Women with variations in physiological functions due to hormones that may effect immune 14 function and (transgender, **pregnant**, breastfeeding) 3. Pregnant (based on history) or lactating. If the possible study participant is female and 15 sexually active and there is a possibility based on history (timing of most recent sexual 16 17 intercourse and timing of menstrual period) that the possible study participant is pregnant, then the participant will be excluded from the study. Rationale: Additional pregnancy testing 18 will further delay the initiation of treatment and will further compromise feasibility of the study 19

20 given limited resources.

Absence of significant clinical disease clinical diseases [e.g., cardiovascular disease (such as coronary artery/vascular disease, stroke), heart disease (such as congestive heart failure, cardiomyopathy, atrial fibrillation), lung disease (such as chronic obstructive pulmonary disease, asthma, bronchiectasis, pulmonary fibrosis, pleural effusions), kidney disease (glomerular filtration rate or GFR less than 60 ml/min/1.73 m2), liver disease (such as

cirrhosis, hepatitis), cancer, major immunosuppression (such as history of transplantation,

1		HIV infection)] based on history. Rationale: Significant clinical diseases can confound
2		interpretation of results for safety and efficacy (e.g., symptomatic viral infection). For
3		example, a patient with known major lung disease such as chronic obstructive pulmonary

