## 6 Power/Sample Size:

7

8 The study is purely exploratory and is not powered to do a formal hypothesis testing. The data 9 from this study will set the basis for large randomized controlled clinical trials to test the safety of 10 mito-MES in the setting of treatment of viral illnesses. In addition, preliminary data will be 11 obtained on the efficacy of Mito-MES to reduce severity of viral illness. More specifically, all the proposed primary endpoints of efficacy are based on objective quantifiable criteria (fever based 12 on thermometer, duration of symptoms based on number of days, severity of viral illness based 13 14 on quantitative summary score that considers at least two independent symptoms of viral illness based on a clinically relevant definition of viral illness made by a physician). The "effect size" of 15 16 the intervention Mito-MES on these quantifiable outcomes of viral illness in humans will be 17 determined. The safety of Mito-MES in the setting of viral illness will be recorded. This is essential information for the design of larger RCT studies. 18

19

20 Based on resources, we enrolled 80 study participants.

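### The mito-MES entry rule on approved alternative treatments contradicts itself, and restoring a lost negation would still leave open whether someone who qualifies for such a treatment but declines or cannot obtain it may enrol.

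*Combined protocol and SAP*

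**What the plan says.** The combined protocol and SAP lists extra inclusion criteria for the mito-MES group under Diagnosis and Key Subject Selection Criteria. Number 3 has two parts.

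- **Opening line.** The participant must be "Ineligible for FDA approved alternative treatments to prevent progression to severe viral" "infection including COVID-19 based on established criteria". The criteria are not set out; a web link to a public-health page on medical conditions stands in for them.
- **Rationale.** It starts "Rationale: If the study participant has confirmed exposure to SARS-CoV-2" and continues "the participant will be allowed to enroll only if he/she is eligible for other FDA approved" "treatments such as monoclonal antibodies or other antivirals for reasons such as personal" "choice, allergies or lack of availability".

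A related rule stands in the paragraph on diagnostic testing just before the exclusion criteria. After a positive SARS-CoV-2 test the "participant will be allowed to continue the study only if not eligible for another FDA approved" treatment for COVID-19. That paragraph also removes participants with a positive test from the final analysis.

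The Screening list records comorbidities, medications, body-mass index, smoking, hypertension and diabetes, among other items. It has no item for eligibility for an approved treatment, or for the reason none was used.

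**The concern.** This is an operative entry criterion, and it decides who may be given an investigational product when an approved option might exist. Its two parts use opposite words for the same condition. The three reasons in the rationale normally explain why a person does not receive a treatment, so they do not fit the word eligible. They also differ in kind from failing a published list of medical conditions. A reader of the trial report could not tell from the plan whether the enrolled participants had no approved option, or had one and did not take it. The point therefore concerns participant protection and the description of who was studied. It does not concern power or error rates.

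**Working it through.** No arithmetic applies, so the three statements are set side by side. The repaired column adds a negation to the rationale only to test whether that removes the conflict. It is not a view on which rule is right. All rows assume confirmed SARS-CoV-2 exposure, because the rationale is limited to that case.

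| Person | Opening line (entry) | Rationale as written (entry) | Rationale with a negation restored (entry) | Continuation rule after a positive test |
|---|---|---|---|---|
| Does not meet the established criteria for any approved option | Admit | Refuse | Admit | Continue |
| Meets the criteria, and is willing and able to take the treatment | Refuse | Admit | Refuse | Stop |
| Meets the criteria, declines | Refuse | Admit | Admit | Stop, if eligibility alone counts |
| Meets the criteria, cannot obtain it | Refuse | Admit | Admit | Stop, if eligibility alone counts |
| Meets the criteria, has an allergy to it | Depends on whether the criteria cover allergy (not stated) | Admit, if still called eligible | Admit | Not stated |

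1. **As written.** The opening line and the rationale disagree in each of the first four rows. The fifth cannot be read from the documents.
2. **With a negation restored.** The first two rows agree. The rows for declining and for non-availability still conflict: the opening line refuses on established criteria, and the rationale admits because choice and availability are among its reasons.
3. **Entry against continuation.** The continuation rule names no reasons. Someone admitted because they declined an option, or could not get it, may count as eligible, and so have to stop, on a positive test. The documents do not say whether eligible has the same meaning in both places.
4. **Other text.** No other section restates the entry rule in a way that settles the question.
5. **Reach.** Mito-MES criterion 1 speaks of contact with a confirmed COVID-19 case, which would bring in most of that group. The Treatments section also allows exposures not confirmed by a test. Power/Sample Size gives 80 participants enrolled but not how many were exposed to confirmed SARS-CoV-2, so the number affected cannot be derived.

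**The case against.** The strongest reply is that this is a drafting slip. The reasons listed make little sense without a negation, and both the opening line and the continuation rule are worded in the negative. That is probably correct about how the sentence arose, and it stands against a reader who infers that the plan set out to recruit two opposite populations. It does not dispose of the rows for declining and non-availability, which conflict after the repair.

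The continuation rule governs a different event from entry and agrees in direction with the opening line. It is therefore not a third entry rule. What remains is that it may apply a narrower idea of eligibility than the rationale does.

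There is one enrolling site, and the physician of record makes the final enrolment decisions (Data and Safety Monitoring Plan). Inconsistent application is thus less likely than the wording alone suggests. The documents do not show that anyone was wrongly enrolled or refused. They also do not show which rule was used.

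It could be said that the age limit and the disease exclusions leave nobody eligible for an approved option. The documents do not establish this. Hypertension, diabetes, body-mass index and smoking are recorded at screening and are not named exclusions, although Protection against Risks describes participants as free from chronic disease. The linked criteria are not available to settle it.

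Finally, the plan states that "The study is purely exploratory and is not powered to do a formal hypothesis testing". That removes any consequence for a formal test, but not the need to state who could be enrolled.

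**Conclusion.** The criterion contradicts itself and should be reconciled. The part that outlasts the likely slip is narrow: whether a person who meets the established criteria but declines treatment, or cannot obtain it, may be enrolled, and whether entry and continuation use the same meaning of eligible. The size cannot be given from the documents, and no sample size, analysis or other stated figure changes.

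Two stronger readings are tempting and are not supported.

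- **Different baseline risk.** A reader might infer that the competing readings select groups at different risk. A difference is possible, but the content of the criteria is not in the documents, and the age limit and disease exclusions already narrow the range.
- **Bias against an untreated group.** The criterion applies only to the mito-MES group, and parts of the text hint at a comparison. Any criterion applied to one group could create imbalance, however it is worded, so this does not follow from the contradiction. The Statistical Analyses section also disclaims formal hypothesis testing.

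The conclusion assumes that the extracted wording is the sponsor's current text, and that established criteria means a published list rather than the investigator's case-by-case judgement. It takes no position on which clinical rule is right.

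**What to change.** - Reconcile the opening line of criterion 3, its rationale and the continuation rule into one consistent rule. State whether personal choice, allergy and availability count, and use eligible in the same sense throughout.
- Report which rule was actually applied at enrolment.
- Because enrolment of 80 is described as done, tabulate descriptively, from existing screening records, how many mito-MES participants met the established criteria and why no approved treatment was used. Comorbidities and medications may allow eligibility to be partly reconstructed. The reason for non-use is not a listed item, so some entries may have to be shown as unknown.

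The cost is a wording change and one descriptive table. No outcome analysis by eligibility status is asked for.

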#### 17 *Retention:*

18

Site investigators are trained about the importance of retention and steps to prevent missing data. To increase subject retention, all subject questions/concerns will be addressed in detail during the consent process. The consent forms will include a statement educating patients about the continued scientific importance of their data even if they discontinue study treatment early. The protocols and informed consent forms will clearly differentiate treatment discontinuation from study withdrawal. There will be constant communication will occur between research staff and participants through phone-call and email reminders prior to all upcoming

1 visits. Several approaches will be implemented to retain patients who fail to actively maintain 2 contact with the investigator (e.g., telephone calls, texts, and emails to the patient and close contacts; vital records search). The study will be conducted through the phone which is easily 3 accessible to participants. All patients who maintain consent will be followed for additional 4 5 outcome information and will remain in the study through the end of the study period for all 6 important safety and efficacy assessments. The only reasons for study withdrawal will be withdrawal of consent and loss to follow-up. Sponsors and investigators will encourage patients 7 8 who discontinue therapy to remain in the study and to continue follow-up for key outcomes. 9 Through these strategies, the investigators have recruited participants with specific interest in participating in research, leading to high rates of retention of study subjects, with high level of 10 11 retention of volunteers in clinical studies even without the need for financial incentives.

12

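### The rule for participants who test SARS-CoV-2 positive does not separate stopping mito-MES from leaving follow-up and, as worded, adds an exit that the Retention section does not allow

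*Combined protocol and SAP*

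**What the plan says.** Two parts of the combined protocol and SAP bear on what happens after a positive test.

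**Key subject selection criteria, paragraph closing the inclusion criteria.** If a test is positive during the study, the "participant will be allowed to continue the study only if not eligible for another FDA approved" COVID-19 treatment. The reason offered is that mito-MES may have useful antiviral and anti-inflammatory effects. The paragraph then says that people with a positive "test will not be included in the final analysis of this PEP trial", and closes: "The data obtained from the participants with a positive SARS-CoV-2 test will set the foundation for future studies of use of" mito-MES in acute COVID-19.

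**Retention.** "The only reasons for study withdrawal will be withdrawal of consent and loss to follow-up". Patients who maintain consent are followed for "outcome information and will remain in the study through the end of the study period for all" important safety and efficacy assessments. Those "who discontinue therapy to remain in the study and to continue follow-up for key outcomes" are to be encouraged. The section also promises: "The protocols and informed consent forms will clearly differentiate treatment discontinuation from study withdrawal".

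Main Parameters of Safety defines the safety parameter as the proportion with adverse events at days 7 and 14. The schedule of events under Participant timeline marks staff and adverse-event assessment at D7, D14 and D21, and nasal swabs daily from D1 to D21.

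**The concern.** Take a participant who tests positive, still consents, can be reached, and is eligible for an approved antiviral. The Retention section keeps this person to the end. The positive-test rule, taken at its word, does not. Staff cannot follow both, and the rule does not say whether it ends dosing or ends participation.

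What is at stake is follow-up of infected, possibly drug-exposed people, in whom later symptoms, hospital stays and adverse events are of most interest. Under the literal reading nothing would be recorded after a switch from mito-MES to an approved antiviral. The data on positives that the plan wants to carry into future treatment studies would, after the test, come only from people not eligible for approved treatment.

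**Working it through.** The plan gives no figure on this point, so there is none to reproduce. The check sets the rules side by side and then counts what one person would lose.

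**Step 1: the two rules**

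| Question | Positive-test rule | Retention section |
|---|---|---|
| What is restricted? | Continuing the study | Study withdrawal, kept apart from stopping treatment |
| Grounds for leaving | Positive test plus eligibility for another approved treatment | Consent withdrawn, or contact lost |
| Follow-up after stopping drug | Not mentioned | Encouraged to continue |

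The rule's ground is neither of the two permitted ones, so as worded it is a third. If *the study* is read as *mito-MES*, the two rules are compatible.

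**Step 2: does another section settle it?** The Missing data section aims to establish vital status, with follow-up for key outcomes, even after a subject decides to stop treatment or participation. That points the same way as Retention, but it concerns the subject's own decision. It does not clearly cover removal by a protocol rule.

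**Step 3: loss per person under the literal reading.** Inputs: contacts at D7, D14 and D21 (schedule of events); diaries D1 to D14; swabs D1 to D21. Assumption, not in the documents: collection stops on the day of the positive test, d, and anything due that day is still collected.

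- Contacts lost = number of {7, 14, 21} greater than d
- Safety-parameter contacts lost = number of {7, 14} greater than d
- Diary days lost = max(0, 14 − d)

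| d | Contacts lost | Of which D7 or D14 | Diary days lost |
|---|---|---|---|
| 1 | 3 | 2 | 14 − 1 = 13 |
| 4 | 3 | 2 | 14 − 4 = 10 |
| 6 | 3 | 2 | 14 − 6 = 8 |
| 7 | 2 | 1 | 14 − 7 = 7 |
| 10 | 2 | 1 | 14 − 10 = 4 |
| 13 | 2 | 1 | 14 − 13 = 1 |
| 14 | 1 | 0 | 0 |
| 21 | 0 | 0 | 0 |

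Over the 21 swab days, 6 (D1–D6) lose three contacts, 7 (D7–D13) lose two, 7 (D14–D20) lose one and 1 (D21) loses none. These are counts of days, not probabilities.

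Two ambiguities in the plan affect the count. The list of staff sessions ends at day 14, so the D21 contact rests on the schedule table alone; without it the maximum is two. Day 0 is study entry in the schedule but exposure in the session list, so the day numbers are relative to whichever origin was used.

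**Step 4: how many people?** The documents do not give the number of positives or their treatment eligibility.

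- In the mito-MES group, criterion 3 requires participants to be "Ineligible for FDA approved alternative treatments to prevent progression to severe viral" infection, which should leave few. The criterion is unclear, though: its rationale speaks of people who *are* eligible, and it lists personal choice and availability, both of which can change after a positive test.
- Criterion 3 is listed for the mito-MES group only. The schedule has a row for drug or no drug, so any untreated participants would not be screened by it. The exclusions for major disease and the age limit of 65 narrow that group as well, without showing that it is empty.

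**Step 5: which results move?** Positives are already outside the final analysis, so the efficacy result is the same under either reading. The plan does not say whether that exclusion also covers safety. If it does, the reported adverse-event proportion is also unchanged and the loss falls on the descriptive data for positives. If it does not, D7 and D14 adverse-event data would be missing for those removed.

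**The case against.** The strongest reply is that there is no real contradiction. The only reason given for the rule is the possible benefit of the drug, which makes sense only for continued dosing. The plan also wants data from positives, and Retention is the section devoted to follow-up. On that view the wording needs tidying and nothing more. Much of this stands: the drug reading is the more likely intent, and nothing in the rule states that data collection stops. It does not dispose of the point, because the plan itself undertakes to separate stopping treatment from leaving the study, and this is a place where it does not.

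It is also fair to say that the affected group may be very small, that the study is exploratory with no formal hypothesis testing, and that it may be over. All of this limits the size of the point.

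A reader might infer more than the documents support:

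- **That the two sections flatly contradict each other.** They do so only if the rule is read literally, and its rationale points the other way.
- **That efficacy is biased by this rule.** Positives are left out of the final analysis whether or not they continue. How that exclusion fits with the intention-to-treat primary analysis is a separate question, which changing this rule would not answer.
- **That safety data were in fact lost.** Nothing shows that the rule was applied literally to anyone.

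**Conclusion.** The point holds as a defect of wording with a possible cost in safety follow-up. The severity is minor. Under the literal reading, a treatment-eligible positive loses up to three scheduled contacts, at most two of which feed the day 7 and day 14 safety parameter, and up to 13 of 14 diary days. This rests on two assumptions: that the rule was applied as a study exit, and that collection ended on the day of the test. The number of people affected is unknown and may be very small.

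**What to change.** Reword the rule so that eligibility for another approved COVID-19 treatment stops mito-MES only. State that diaries, scheduled remote contacts and adverse-event follow-up then continue under the Retention section unless consent is withdrawn. Report adverse events, severity and hospitalisation descriptively for all positives, noting any switch to an approved treatment and when it happened.

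If follow-up is still open, the cost is one wording amendment, with the IRB approval that the plan requires for any amendment, and at most three contacts per affected person. Those contacts are already in the schedule, and no new procedure is needed.

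The past tense in the Summary and the statement under Power/Sample Size that 80 were enrolled suggest that follow-up may be complete. In that case lost data cannot be recovered. The report should state how many positives were stopped under this rule and on which day contact ended. That is one line, and zero would be a useful answer.

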12		contraception. Rationale: Since the study drug (mito-MES) has not been studied in pregnant
13		women, women and men of child bearing potential should use a barrier method that
14		prevents pregnancy in combination with a highly effective method of contraception. Highly
15		effective methods are:
16		oral contraceptive
17		
 
Use of condoms during any sexual intercourse during the study period
 

18		intrauterine device
19		intrauterine hormonal releasing systems
20		Bilateral tubal ligation/occlusion
21		• Vasectomized partner provided that partner is the sole sexual partner of the participant and
22		that the vasectomized partner has received medical assessment confirming surgical
23		success.
24		
25	Giv	ven how essential it is to start potential treatment as soon as possible after high-risk exposure
26	to	a viral infection, participants will be allowed to participate without waiting for the results of a

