## 4 Participant timeline

5

6 Study Outline/Schedule of events/ Participant Timeline: Potential participants are screened for

7 study eligibility by telephone ± video link; consenting individuals undergo a remote (via video-

8 link or, if not feasible, by telephone) baseline visit (day 1) within 24 h. Subsequent remote visits

9 occur on days 1, 7, 14. The full schedule of events is shown in Table 4.

Timepoints (D0 is the day of	Before (<) D0	D1	D7	D14	D21
study entry)	or D0-D4				
Eligibility assessment	х				
Informed consent	X				

Dispensation of study drug (Mito	- X				
MES arm)					
Assessment by study staff		Х	X	х	х
Drug/no drug treatment					
Adherence assessment		Daily D1	-14		
Symptoms assessment		Daily D1	-14		
Temperature assessment		Daily D1	-14		
Concomitant medication					
assessment					
Self-collected Nasal swab	Х	Daily D1	-D21		
(PCR/rapid antigen test)					
Adverse event assessment			Х	Х	X

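### Participants who test SARS-CoV-2 positive during the study are dropped from the final analysis, which contradicts intention-to-treat as primary and removes detected prophylaxis failures from the endpoints

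*Combined protocol and SAP*

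**What the plan says.** The closing paragraph of the inclusion criteria states that "participants will be allowed to participate without waiting for the results of a" diagnostic test. The rule that follows has this trigger: "If a participant has a positive SARS-CoV-2 during the study". Staying in is then made conditional, in that such a "participant will be allowed to continue the study only if not eligible for another FDA approved" treatment. The paragraph goes on to say that for these people a positive result has a further consequence: those with a positive "test will not be included in the final analysis of this PEP trial". Their data are set aside for later work on acute treatment.

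Other parts of the document bear on this:

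- **Sensitivity analyses** (statistical section): intention-to-treat is named as the primary analysis.
- **Secondary measures of efficacy**: the list includes PCR-confirmed SARS-CoV-2 infection with symptoms, and infection confirmed by any FDA-approved test.
- **Participant timeline**: the row "Self-collected Nasal swab" runs daily from D1 to D21.
- **Additional criteria for the mito-MES group**: criterion 1 requires "contact with a confirmed COVID-19 case within the past 1-4 days prior to study entry". The general criteria and the Treatments section accept exposure to any suspected virus.
- **Missing data**: a death linked to SARS-CoV-2 is not treated as missing for the primary outcome.
- **Retention**: withdrawn consent and loss to follow-up are the only grounds for leaving the study.
- **Power/Sample Size**: 80 people were enrolled, a number set by resources.

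**The concern.** In a post-exposure prophylaxis study, a SARS-CoV-2 infection under treatment is the failure that the study exists to count. A rule that removes people once that failure is detected makes the analysis set depend on the outcome. Intention-to-treat is meant to prevent exactly this.

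The study does no formal testing, so no type I error rate is at stake. Descriptive rates and an effect size for later trials are its main product. After the exclusion, the illness rate no longer describes the 80 people enrolled. If groups are compared, which the statistical section leaves unclear, the rule could also shrink or hide an effect on SARS-CoV-2.

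**Working it through.** **Text.** The rule is triggered by a positive test during the study, and swabs run to day 21. No baseline cut-off, pre-dose restriction or separate analysis set appears anywhere. Two readings of who is excluded follow from the wording:

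- All positives. PCR-confirmed symptomatic SARS-CoV-2 is then 0/n whatever the data show.
- Only positives who continue. That endpoint loses those cases but need not be zero.

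On both readings, detected cases leave the any-symptom and severity endpoints. The Missing data section fits poorly with this, since a test-positive person who died of SARS-CoV-2 would count as observed there and yet could be absent from the analysis. The statement that primary outcomes are assessed in all participants is weaker support, because it concerns data availability.

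**Figure in the plan.** The 80 rests on resources. No alpha, power, effect size or event rate is given, so there is nothing to reproduce.

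**Size, single arm.** All inputs are assumed:

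- p = true share ill, set at 0.30
- f = share of the ill who are SARS-CoV-2 positive
- s = share of SARS-CoV-2 infections with symptoms
- e = share of infections detected and excluded, taken as independent of symptoms

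The infected share of the cohort is pf/s. Exclusion removes e·pf of the ill and e·pf/s of all participants, so

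rate after exclusion = p(1 − ef) / (1 − e·pf/s).

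Example with e = 1, f = 0.5, s = 1: 0.30 × 0.5 / (1 − 0.15) = 0.15/0.85 = 17.6%.

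| e | s | f = 10% | f = 25% | f = 50% | f = 75% |
|---|---|---|---|---|---|
| 1 | 1 | 27.8% | 24.3% | 17.6% | 9.7% |
| 1 | 0.5 | 28.7% | 26.5% | 21.4% | 13.6% |
| 1 | 0.25 | 30.7% | 32.1% | 37.5% | not run |
| 0.5 | 1 | 28.9% | 27.3% | 24.3% | 21.1% |
| 0.5 | 0.5 | 29.4% | 28.4% | 26.5% | 24.2% |
| 0.5 | 0.25 | not run | not run | 32.1% | not run |

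The result equals p when s = p, is lower when s > p and higher when s < p. Since p is a weighted average of s and the illness rate in everyone else, s > p holds exactly when SARS-CoV-2 positives are ill more often than the rest. That is the likelier case.

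**PCR endpoint.** Take n = 80, p = 0.30, f = 0.5, s = 0.7, with all positives by PCR. Symptomatic cases = 80 × 0.30 × 0.5 = 12, and infections = 12/0.7 = 17.1.

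- No exclusion: 12/80 = 15%.
- All positives excluded: 0/62.9.
- Only the half who continue excluded: 6/71.4 = 8.4%.

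**Second parameterisation, also assumed.** Let q be the share testing positive and o the illness rate in test-negatives. The rate in all enrolled is qs + (1 − q)o; after exclusion of all positives it is o. With q = 30%, s = 60–80% and o = 5–10%, 56 of 80 are analysed, the rate is 5–10% instead of 21.5–31%, and 80qs = 14.4 to 19.2 events are lost. These inputs have s well above o, so they can show only understatement.

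**Hypothetical comparison of 40 and 40.** Take positivity 50% and 20%, s = 70%, o = 5%. The full rates are 0.5 × 0.7 + 0.5 × 0.05 = 37.5% and 0.2 × 0.7 + 0.8 × 0.05 = 18%, a difference of 19.5 points. After exclusion both are 5% and the difference is 0.

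**The case against.** The best defence is that the paragraph was aimed at people already infected at entry. It sits in the eligibility section, opens with enrolment before a test result is known, and separates prophylaxis data from acute-treatment data. Read that way, cases arising after entry would stay in. The aim is reasonable, but the text speaks of a positive test during the study and no other section narrows it, so an analyst following the plan would remove later cases too.

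Other points have some force:

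- Intention-to-treat appears in a single clause under Sensitivity analyses, with no defined set and no randomisation described. The analysis set is therefore undefined as well as inconsistent, but that does not remove the contradiction.
- The Retention conflict may be only loose wording, if continuing the study means continuing the drug; that section follows people who stop treatment. It needs reconciling, and the main point does not depend on it.
- The Missing data text on death does not define an analysis set, so it is supporting evidence only.
- The direction of bias is not fixed by the documents, and the 37.5% case needs 0.30 × 0.5/0.25 = 60% of the cohort infected.
- Removal may depend on symptoms: the efficacy sections say the study pays for no diagnostic tests and that results may be missing for some, while the schedule has daily swabs. If people with symptoms are tested more, those removed are more often ill, which pushes towards understatement.

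**Conclusion.** The concern holds. As written, the plan excludes people on a post-entry outcome, against its own primary analysis, and this must be fixed. One conclusion needs no assumed rates: if all positives are excluded, the PCR-confirmed symptomatic SARS-CoV-2 endpoint is zero whatever the drug does.

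The effect on the illness rate depends on quantities that the documents do not give. With an assumed true rate of 30%, the scenarios run from 9.7% to 37.5%. They stay close to 30% when SARS-CoV-2 causes a small share of illness or few infections are removed. That share could be small, because any suspected virus qualifies, or large, because the mito-MES criterion requires a confirmed COVID-19 contact. Understatement is likelier than overstatement but not certain.

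**What to change.** 1. Delete the exclusion from the final analysis and keep every enrolled participant in the primary intention-to-treat analysis.
2. Count a positive test as an event only for the test-confirmed endpoints. For the any-symptom and severity endpoints, count positives by their recorded symptoms.
3. Address infection at entry by a sensitivity analysis that leaves out people positive on a swab taken before the first dose, and report how many had no such swab. Excluding entry positives from the main analysis would need a reliable pre-dose swab in everyone, so it is better placed here.
4. First reconcile Day 0. The schedule of events has "Timepoints (D0 is the day of" study entry, whereas Sessions by study staff defines it as the day of exposure. Because drug could be supplied for "immediate use after anticipated exposure to confirmed case of SARS-CoV-2", also report how many pre-dose swabs came before exposure.
5. Reconcile the condition for continuing the study after a positive test with the Retention section, so that outcome data on positives are kept. Who may continue treatment is a clinical matter and is not addressed here.
6. A secondary point: inclusion criterion 5 asks for at least four tests when results are negative, so it too selects on test results. Do not use it to define the analysis set; report tests per participant and anyone left out under it.

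The cost is protocol and SAP wording, plus keeping or retrieving outcome data for positives who stopped. No extra patients are needed. The illness rate may look less favourable, and some infections incubating at entry will count as events; the sensitivity analysis in step 3 shows how much of the rate comes from infections already detectable before the first dose.
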